4.6.2. Analysis Methods

Protocol-defined virologic rebound, Snapshot and TLOVR approach

Tabulations (numbers and proportions) per time point will be provided for the Snapshot outcomes (success, failure, no data within window). Tabulations (numbers and proportions) will also be provided for the categorical parameters (virologic rebounders and TLOVR), through Week 96. The exact 2-sided 95% CIs around in each treatment group will be calculated by the Clopper-Pearson method for Protocol-defined virologic rebound, Snapshot virologic success and virologic failure, and TLOVR response. Bar charts will be presented for virologic rebounders and Snapshot outcomes.

Time to virologic rebound

Time to virologic rebound will be graphically presented by means of Kaplan-Meier curves and a Cox proportional hazards model will be fit separately for each treatment group. Terms included in the model for the initial D/C/F/TAF group will be bPI at screening, and any pre-dose (screening phase) viral load ≥ 50 copies/mL (Yes/No). Terms in the model for the Late Switch group will be bPI at screening and any pre-D/C/F/TAF dose viral load ≥ 50 copies/mL (Yes/No).

Immunologic Change

Descriptive statistics (n, mean (se), median, and ranges) per time point will be provided for the continuous parameters, CD4 cell count actual values and change from reference. CIs for the means and mean changes will be calculated. The changes from reference (NC=F) of the two treatment arms and the 95% CIs at Week 96 will be constructed using ANCOVA separately for each treatment group, including term for bPI at screening and reference CD4+ value as a covariate. A sensitivity analysis using Mixed-effects model for repeated measures (MMRM) approach will also be performed separately for each treatment. The model will include change from reference as a response variable (observed case), terms for bPI at screening, visit, and the corresponding reference value as a covariate. An unstructured covariance matrix will be used to model the correlation among repeated measurements.

Cross-tabulations of Week 96 CD4 cell count versus reference will be provided using the categories: < 200 , $200 \leq x < 350$, $350 \leq x \leq 500$, > 500 cells/mm³

Viral Blip

Tabulations (numbers and proportions) of subjects with 0, 1, 2, 3 or more blips will be presented. Further, FDA Snapshot outcome at Week 96 and descriptive statistics of adherence by subjects with rebound, Blip or No Blip will be presented. CMH (nonzero correlation) test will be used for comparison within

treatment group of compliant (>95%), Snapshot success as well as for Snapshot failures. Blips will also be presented graphically.

Per Protocol Analysis

The key secondary endpoints will also be analyzed on the per protocol (PP) population. Details on which outputs are included for the PP population will be provided in the Data Presentation Specifications (DPS) document.

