## 4.1. Inclusion Criteria

Each potential subject must satisfy all of the following criteria to be enrolled in the study.

- 1. The ability to understand and sign a written ICF, which must be obtained prior to initiation of study procedures.
- 2. Currently being treated with a stable ARV regimen consisting of a bPI (limited to DRV once daily with rtv or COBI, ATV with rtv or COBI, or LPV with rtv) combined with FTC/TDF only, for at least 6 consecutive months preceding the screening visit.

Subjects treated with the combination DRV + COBI + FTC/TDF and having completed the required visits in the GS-US-216-0130 study, and who are fulfilling the present protocol criteria, will be given the option to participate in this study.

Note: A change in pharmacokinetic booster (ie, rtv or COBI) will be allowed provided such a switch occurred no less than 1 month prior to the screening visit.

- 3. Documented evidence of being virologically suppressed while on a stable ARV regimen prior to screening: at least 1 plasma HIV-1 RNA measurement <50 copies/mL (or HIV-1 RNA undetectable by a local HIV-1 RNA test) occurring between 12 and 2 months prior to the screening visit while on the stable ARV regimen and have HIV-1 RNA <50 copies/mL at the screening visit.
  - A single viral load elevation of ≥50 copies/mL and <200 HIV-1 RNA copies/mL after previously reaching viral suppression ('blip') within 12 months prior to screening is allowed, provided a subsequent viral load measurement is <50 HIV-1 RNA copies/mL (or HIV-1 RNA undetectable by a local HIV-1 RNA test) prior to screening.
- 4. Screening eGFRcr  $\geq$ 50 mL/min according to the Cockcroft-Gault formula for creatinine clearance.
- 5. Absence of history of failure on DRV treatment and absence of DRV RAMs (including V11I, V32I, L33F, I47V, I50V, I54M, I54L, T74P, L76V, I84V, L89V), if documented historical genotypes are available.
  - If no historical genotype is available, the subject can be included, provided no previous failure on DRV treatment has been documented.
- 6. Normal ECG at screening (or if abnormal, determined by the investigator to be not clinically significant).
- 7. Screening hepatic transaminases (alanine aminotransferase [ALT] and AST) ≤5 x upper limit of the normal range (ULN).
- 8. Screening direct bilirubin  $\leq 1.5 \text{ x ULN}$ .
  - Subjects with documented Gilbert's Syndrome or hyperbilirubinemia due to ATV therapy may have total bilirubin up to 5 x ULN.

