2.5. Visit Windows

2.5.1. Trial Phases

Phases will be constructed for each subject as follows for adverse events, concomitant therapies, and for the determination of the worst-case/toxicity/change in the cross-tabulations.

Trial phase	Start date	End date
Screening	Minimum of Date of signing the informed consent and Date of the screening visit	1 day before start of treatment
Comparative Treatment Phase	Date of the first intake (after randomization)	
For initial D/C/F/TAF subjects, in order of priority:
 
 - Week 48 visit date; if missing then - Projected Week 48 visit date, where projected Week 48 visit date = baseline visit date + (7 *48) 
For late switchers: Date of first D/C/F/TAF intake-1 day
 
In case of withdrawal use:
 
 - Minimum(last intake date of study drug, study withdrawal date) + 2 days
Extended Treatment Phase (Extension)	Last Date of Comparative Treatment Phase +1 day	
 - Week 96 visit date; if missing then - Projected Week 96 visit date, where projected Week 96 visit date = baseline visit date + (7 *96) 
In case of withdrawal use:
 
 - Minimum (last intake date of study drug, study withdrawal date) + 2 days
Follow-up	End of last treatment phase +1 day	Trial termination date for all groups (date of last contact)

Data up to each subject's Week 96 visit are in scope for this analysis, DXA data (DP domain) up to Week 96 visit+28 days, and if applicable, any (confirmatory) viral load or genotype/phenotype results immediately subsequent to Week 96 (up to 6 weeks).

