2.5.2. Analysis Time points

All visits/assessments will be allocated to the following time points as per the table below, based on the number of days in the study, calculated as “assessment date – start date of comparative treatment phase + 1 day” for Comparative Treatment/Extended treatment and Follow-up phase.

The following time intervals will be used for reporting of efficacy as well as safety data:

Phase	Visit	Target day	Analysis time point	Time interval (days)
Screening	1	-∞	Screening	< Day 0
Comparative Treatment Phase	2	1	Baseline ^a	≤Day 1
	3	15	Week 2	Day 2 – Day 21
	4	29	Week 4	Day 22 – Day 42
	5	57	Week 8	Day 43 – Day 70
	6	85	Week 12	Day 71 – Day 126
	7	169	Week 24	Day 127 – Day 210
	8	253	Week 36	Day 211 – Day 294
	9	337	Week 48 ^b	Day 295 – Day 378
Extended treatment phase (Extension)	10	421	Week 60 (Week 12)	Day 379 – Day 462
	11	505	Week 72 (Week 24)	Day 463 – Day 546
	12	589	Week 84 (Week 36)	Day 547 – Day 630
	13	673	Week 96 ^c (Week 48)	Day 631 – Day 714
Follow-up	14	31	Follow-up	Day 1 onwards

^a Only the record closest to target day 1 will be allocated to analysis time point ‘Baseline’, all records prior to day 1 are assigned to ‘Screening’.

For DXA scans a scan up to 28 days post-baseline was used as a baseline scan.

^b DXA scan up to 28 days post-Week 48 was used as the Week 48 scan

^c DXA scan up to 28 days post-Week 96 was used as the Week 96 scan.

Note, for Initial Switchers to D/C/F/TAF, period “Baseline-Week 96” will include visits from Comparative treatment phase and Extended treatment phase.

Unless specified otherwise, if two visits fall within the same interval, the one closest to the target day will be used for the analysis displays and graphics in order to have only one evaluation per subject per analysis time point. However, all data will be presented in the listings. If distances of both visits to the target day are equal, the visit latest in time will be used. If multiple visits that fall within the same analysis window have the same date/time, the one with the highest sequence number will be used.

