2.7. Definition of Subgroups

2.7.1. Subgroups for Efficacy Analyses

- Adherence based on D/C/F/TAF (i.e., from reference) drug accountability (>95%: adherent, $\leq 95\%$: non-adherent, missing/unknown)
- Reference viral load
 - For Initial D/C/F/TAF group the screening and baseline viral load
 - <50; if all screening and baseline viral load values are below 50 copies/mL
 - ≥ 50 ; if at least one viral load value during screening or baseline ≥ 50 copies/mL)
 - For Late Switch group, the reference viral load
 - <50 copies/mL
 - ≥ 50 copies/mL
- CD4+ count at reference (<200, ≥ 200 [200 $\leq x < 350$, 350 $\leq x \leq 500$, >500] cells/mm³)
- Race (American Indian or Alaska Native, Asian, Black or African American, White, Native Hawaiian or other Pacific Islander, Other, non-Black or African American)
- Ethnicity (Hispanic or Latino, non-Hispanic or Latino)
- Gender (Female, Male)
- Age group (≤ 50 , >50 years)
- Region (Europe, North America)
- Re-classified bPI at screening (see section 2.5):
 - DRV once daily with rtv or COBI; ATV with rtv or COBI; LPV with rtv
 - ATV with rtv or COBI, or LPV with rtv
 - DRV with rtv; DRV with COBI
- Booster at screening (ritonavir or cobicistat)
- Number of previous ARVs used (3, 4, 5, 6, 7, >7) and previous PI, N(t)RTI or NNRTI used (0, 1, 2, 3, 4, >4)

- Previous ARV failure and previous PI, N(t)RTI or NNRTI failure (0, ≥ 1)
- WHO Clinical Staging of HIV/AIDS
- Viral blip (see section 4.6.1) during first 48 weeks:
 - Yes, if subject experience at least 1 viral blip during the first 48 weeks of the study
 - No, otherwise
- For the Late Switch group only:
 - Protocol-defined virologic rebound during first 48 weeks
 - Yes, if subject experience a protocol-defined virologic rebound during the first 48 weeks of the study
 - No, otherwise

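### The initial-arm Cox covariate for pre-dose viraemia is limited to the screening phase, so read literally it omits the Day 1 baseline value that SAP 2.7.1 counts

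*SAP*

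**What the plan says.** SAP 4.6.2 (Time to virologic rebound) plans Kaplan-Meier curves and a Cox model fitted separately in each group. For subjects who switched at the start: "Terms included in the model for the initial D/C/F/TAF group will be bPI at screening, and any pre-dose (screening phase) viral load" of at least 50 copies/mL (Yes/No). For the control subjects who switched later: "Terms in the model for the Late Switch group will be bPI at screening and any pre-D/C/F/TAF dose viral load" of at least 50 copies/mL, with no phase named.

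Three other SAP sections bear on the words in parentheses:

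- SAP 2.5.1 ends the screening phase "1 day before start of treatment" and starts the comparative phase on the date of first intake. It opens by stating what the phases are for: "Phases will be constructed for each subject as follows for adverse events, concomitant therapies", and worst-value cross-tabulations.
- SAP 2.5.2 introduces its table with "The following time intervals will be used for reporting of efficacy as well as safety data". Screening is one row; Baseline, with target day 1, is a separate row under the comparative treatment phase.
- SAP 2.7.1 defines the reference viral load subgroup with "For Initial D/C/F/TAF group the screening and baseline viral load". A subject is in the upper category if any of those values is 50 or more.

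Protocol section 5 requires all Day 1 tests to be done before the first dose, which must follow within 24 hours of the baseline visit. Protocol 4.1, criterion 3, requires HIV-1 RNA below 50 "copies/mL at the screening visit".

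**The concern.** The covariate is meant to separate subjects who were viraemic before starting D/C/F/TAF from those who were not. Because entry required a screening value below 50, the baseline sample is where most pre-dose values of 50 or more would be expected. The SAP anticipates such values: Attachment 1 removes subjects with baseline RNA of 50 or more from the per-protocol set. A rule confined to the screening phase leaves out that sample.

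Since the models are fitted within group, they contain no treatment term. They yield only the hazard ratios for bPI and for prior viraemia. If baseline-viraemic subjects sit in the No category, the second ratio does not measure what its label says, and it will not match the 2.7.1 subgroup table for the same arm.

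**Working it through.** The plan gives no figure for this covariate, so there is none to reproduce. The check sets the definitions side by side, follows one subject through them, and then bounds the size.

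**1. Where the Day 1 baseline value counts (initial arm)**

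| Place | Values used | Baseline value counted? |
|---|---|---|
| SAP 4.6.2, Cox term | pre-dose, qualified as screening phase | No, if the qualifier is applied |
| SAP 2.5.1, phases | screening ends the day before first dose | Outside screening when dosing is on the same day |
| SAP 2.5.2, time points (efficacy and safety) | Screening and Baseline are separate rows | Baseline, not Screening |
| SAP 2.7.1, subgroup | screening and baseline | Yes |
| SAP Attachment 1, PP exclusion | baseline | Yes |

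**2. One subject traced through the rules**

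Take a subject with screening RNA below 50, baseline RNA of 50 or more, and a first dose on the day of the baseline visit. SAP 2.5.2 gives study day = assessment date − first-dose date + 1 = 0 + 1 = Day 1. The record is Baseline under 2.5.2 and after the end of screening under 2.5.1. The 2.7.1 subgroup puts this subject in the upper category; the Cox term, read literally, codes No.

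If the first dose is on the next day, the study day is −1 + 1 = Day 0. By date alone, 2.5.1 would put the sample in screening. Under 2.5.2, the table that covers efficacy, it is still the record nearest Day 1 and so, on the natural reading, still Baseline.

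**3. Size**

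The documents do not report how many subjects had a baseline value of 50 or more. With the planned 734 in the arm and an assumed proportion p, the number coded differently is 734 × p:

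- p = 1%: 734 × 0.01 = 7.3
- p = 2%: 734 × 0.02 = 14.7
- p = 3%: 734 × 0.03 = 22.0
- p = 5%: 734 × 0.05 = 36.7

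For scale, the design's 4% rebound rate through Week 48 implies 734 × 0.04 = 29.4 rebounders in this arm. The misclassified group could be of the same order as the number of events, although only 1% to 5% of subjects move.

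**4. Direction**

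If baseline viraemia raises the hazard of rebound (plausible, but not stated in the documents), coding these subjects No raises the hazard in the comparison group and pulls the ratio towards 1. The net effect also depends on who remains in the Yes category, so its sign and size cannot be derived from the documents.

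**The case against.** The strongest reply is that the sentence opens with any pre-dose value. Protocol section 5 makes the baseline sample pre-dose, so the parenthesis may be a loose label for the whole pre-treatment period. On that reading 4.6.2 already agrees with 2.7.1. This stands to the extent that the text is ambiguous and does not prove an intended exclusion. It does not remove the problem: the SAP offers no broader meaning of screening phase, its efficacy table separates Screening from Baseline, and two programmers could code the term differently.

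It is also fair that baseline viraemia is handled elsewhere, in the 2.7.1 subgroup and the per-protocol exclusion, and that SAP 1.3 and 4.4.1 make the Week 96 efficacy results descriptive. That limits the consequence.

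A reader might go further in three ways that the documents do not support:

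- **Coding turns on the day of first dose.** The flip between same-day and next-day dosing comes only from 2.5.1, whose stated uses do not include efficacy covariates. It does not arise under 2.5.2.
- **Almost nobody would be coded Yes.** Any such count needs an assumed share of same-day dosing. It also leaves out subjects with 50 or more at screening. Attachment 1 lists that deviation (item 2), and its footnote describes subjects randomized on a retest below 50. The screening-phase wording captures those subjects.
- **The late-switch term is wrong too.** Using any value before the switch is a legitimate modelling choice; a Cox term need not equal a subgroup factor, and no comparison of the two hazard ratios is planned. Replacing it with the single pre-switch reference value would probably give a sparse covariate, because switching required adequate viral load (SAP 1.2) and a Week 48 value of 50 or more led to a retest before the switch (Protocol, Time and Events Schedule).

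**Conclusion.** The point holds for the initial D/C/F/TAF arm only. As written, the Cox covariate omits the baseline value, which is drawn before dosing, is the likeliest place for pre-dose viraemia given the entry rule, and is counted in the SAP's own factor for the same arm. Subjects viraemic at baseline but not at screening go into the comparison group. About 7 to 37 of 734 would be affected if 1% to 5% had such a value; that range is assumed, and 734 is the planned arm size.

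This is a minor correction. It touches one hazard ratio in a descriptive model on the ITT set; the per-protocol set excludes these subjects anyway. No conclusion about noninferiority, and none of the planned rebound proportions with exact intervals, depends on it.

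**What to change.** In SAP 4.6.2, for the initial arm, replace the pre-dose (screening phase) wording with: *any screening or baseline (pre-dose) viral load ≥50 copies/mL (Yes/No)*, and refer to SAP 2.7.1 so that the model and the subgroup table use one derivation. Leave the late-switch term as it is.

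The cost is one phrase in the SAP and the matching line in the programming specification. The values are already collected and already derived for the subgroup. The change should be made before the Week 96 models are run, so that the coding is not settled at programming.

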4. EFFICACY

4.4. Analysis Specifications

4.4.1. Level of Significance

No formal statistical tests will be calculated. All results will be descriptive.

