4.6.1. Definitions

Virologic Rebound

Virologic rebound is defined as:

- subjects who show confirmed HIV-1 RNA $\geq 50/20/200$ copies/mL from the reference up to, and including Week 96,
- subjects who discontinued prematurely (irrespective of reason) for which the last available (single) HIV-1 RNA value on treatment was $\geq 50/20/200$ copies/mL.
- any subject with last available on-treatment HIV-1 RNA $\geq 50/20/200$ copies/mL at the study cut-off of Week 96 (i.e., any last viral load [re]test having occurred no later than 6 weeks after Week 96)

All other situations are considered non-rebounders.

Snapshot approach (applying 20/50/200 copies/mL as threshold)

The Snapshot approach will classify subjects into 3 outcome categories: “virologic success”, “virologic failure” and “No viral load data”. Several subcategories of the outcome will also be presented in the analysis and are shown below. The categories below are mutually exclusive such that a subject will be included in one (sub)category. If a subject discontinues in the time window but also has an HIV-RNA value in the time window then the viral load data will be used to classify the subject’s category.

- Virologic success:
 - Last available HIV RNA $< 20/50/200$ copies/mL in the Week 96 visit window (Week 90-102)
- Virologic failure:
 - Last available HIV RNA $\geq 20/50/200$ copies/mL in the Week 96 visit window (Week 90-102)
 - Virologic failure leading to discontinuation

- Discontinued due to other reason (i.e. other than AE/death or virologic failure) and last available HIV-RNA $\geq 20/50/200$ copies/mL
- No viral load data in the Week 96 visit window
 - Discontinued due to AE/death (subjects will be classified in this category if discontinued prior to Week 96 window regardless of HIV-RNA level)
 - Discontinued due to other reason (i.e. other than AE/death or virologic failure) and the last available HIV RNA $< 20/50/200$ copies/mL (or missing)
 - Missing data during the Week 96 visit window but on study

The following threshold criteria are considered:

- < 20 : HIV RNA below 20 copies/mL (target not detected or target detected)
- < 50 : HIV RNA below 50 copies/mL
- < 200 : HIV-RNA below 200 copies/mL

Imputations for missing values

The following imputation method is used to calculate **virologic response** at a given time point:

- observed case: subjects with a missing value are disregarded in the analysis for that time point.

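### The CMH test of Week 96 Snapshot failure across rebound, Blip and No Blip is largely decided by how the groups are defined and tells almost nothing about blips

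*SAP*

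**What the plan says.** SAP 4.6.2 (Viral Blip) states that "FDA Snapshot outcome at Week 96 and descriptive statistics of adherence by subjects with rebound, Blip or No Blip will be presented". The next sentence adds that "CMH (nonzero correlation) test will be used for comparison within" "treatment group of compliant (>95%), Snapshot success as well as for Snapshot failures". That makes three tests in each treatment group: compliance, Snapshot success and Snapshot failure. The SAP gives no row order, scores or threshold pairing. It has no rule for a subject with both a blip and a rebound, and it does not say whether the test covers all three groups.

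SAP 4.6.1 counts a subject as a rebounder on any of three limbs:

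1. a confirmed value at or above the threshold;
2. early discontinuation for any reason with the last on-treatment value at or above the threshold;
3. "any subject with last available on-treatment HIV-1 RNA" at or above the threshold at the Week 96 cut-off, which allows retests up to 6 weeks later.

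It defines three Snapshot failure categories:

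- A: the last value is at or above the threshold, measured in "copies/mL in the Week 96 visit window (Week 90-102");
- B: "Virologic failure leading to discontinuation";
- C: discontinuation for another reason with the last value at or above the threshold.

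SAP 4.4.1 states: "No formal statistical tests will be calculated. All results will be descriptive". SAP 1.3 adds that no formal hypothesis is tested at Week 96.

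**The concern.** If the outcome is largely built into one of the groups, a test of association between group and outcome measures that construction. The p-value would appear under the Viral Blip heading, where a reader could take it as evidence that blips go with virologic failure. The comparison that would bear on that question is Blip against No Blip, and there both failure rates are close to zero by definition. The missing specifications add a second problem, because the p-value changes with choices that the SAP leaves open.

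**Working it through.** **Step 1. Compare the definitions at one threshold.**

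| Snapshot failure category | Rebound limb | Contained? |
|---|---|---|
| A. High last value, Weeks 90-102 | 3. High last value up to Week 96 + 6 = Week 102 | Yes |
| C. Stopped for other reason, high last value | 2. Stopped for any reason, high last value | Yes |
| B. Stopped for virologic failure | No matching limb; no viral-load condition | Usually, through limb 1 or 2 |

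SAP 4.4.2 restricts HIV-1 RNA to on-treatment data for the whole analysis, so both definitions draw on the same values. Category B can escape. For example, a subject with confirmed values of 50-199 copies/mL who stops for virologic failure is a failure at the 200 threshold but not a rebounder at 200.

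The converse does not hold. A confirmed rebounder who re-suppresses is a Snapshot success. A subject who stops for an AE with a high last value before the Week 96 window is a rebounder but is classed as having no viral load data.

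**Step 2. Inputs for an illustration.** The documents give no figure for this test and no Week 96 counts.

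- Planned arm sizes are 734 and 367 (SAP 1.2), and the rebound assumption is 4% through Week 48 (SAP 1.4). As a check on these inputs, SE = √[0.04 × 0.96 × (1/734 + 1/367)] = 0.01253 and 0.04/0.01253 − 1.96 = 1.23. Power is 89.1%, against the stated 89%.
- Rebounders: 4% of 734 = 29.
- Blip subjects: 10% of 734 = 73 (assumed; 3% and 20% were also run).
- No Blip: 734 − 29 − 73 = 632.

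**Step 3. The statistic.** Q = (N − 1)r² on 1 df. With f failures, all among rebounders whose score is s:

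r² = (f/N)(s − x̄)² / [(1 − f/N) × var(x)]

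With rebound = 1, Blip = 2, No Blip = 3 and f = 1:

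- x̄ = (29 + 146 + 1,896)/734 = 2.8215
- var(x) = 6,009/734 − 2.8215² = 0.2256
- Q = 733 × 0.001362 × 1.8215² / (0.99864 × 0.2256) = 14.7, p = 0.00013

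**Step 4. Other orders and counts** (29/73/632, all failures among rebounders).

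| Row order | 1 failure | 2 failures | 3 failures |
|---|---|---|---|
| rebound, Blip, No Blip | p = 0.00013 | 5.7e-8 | 2.9e-11 |
| Blip, No Blip, rebound (alphabetical) | 0.0040 | 4.6e-5 | 5.8e-7 |
| No Blip, rebound, Blip | 0.22 | 0.081 | 0.032 |

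For N = 367 with 15 rebounders and 37 Blip subjects, one failure in the first order gives p = 0.00016. Over rebound rates of 1-5% and blip rates of 3-20%, one or more failures gave p ≤ 0.0023 in the first order and p ≤ 0.016 in the alphabetical order. In every one of these tables Blip and No Blip both have 0% failure.

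**Step 5. Where the pattern breaks.**

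- With no failures, Q is undefined.
- With one rebounder failure plus 2 or 3 category B failures among No Blip subjects, p = 0.075 or 0.17 in the first order.
- If only Blip and No Blip are compared, the table is 0 against 0 apart from stray category B cases. One such case among the 73 Blip subjects gives p = 0.003; one among the 632 No Blip subjects gives p = 0.73.

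**Step 6. The Snapshot success test.** Assume 3 of 73 Blip (4.1%) and 30 of 632 No Blip (4.7%) subjects are non-successes. With 1, 3 or 5 non-successes among 29 rebounders, p = 0.69, 0.35 and 0.029. The definitions do not decide this result.

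**The case against.** The strongest reply is that the circularity needs three conditions that SAP 4.6.2 does not state.

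- **Groups.** The three groups are named for the display, and the test sentence does not repeat them. It does follow directly, so three groups is the natural reading.
- **Precedence.** Only a confirmed rebound is excluded from being a blip, and blips are counted up to the lower limit of the Week 96 window. A subject with an earlier blip and a single high value in Weeks 90-102 meets both definitions. If Blip took precedence, Blip subjects could be failures.
- **Threshold.** Snapshot and rebound use 20, 50 and 200 copies/mL, but blips use only 50 and 200. With Snapshot at 20 and groups at 50, non-rebounders can fail.

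These points stand, and they are why the conclusion is conditional. They also show that the test is under-specified.

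A reader might infer that every Snapshot failure is a rebound, or that significance is guaranteed. Category B and Step 5 rule out both. A reader might also infer that the Snapshot success and compliance tests are circular. Step 6 shows that the success test is only partly constrained, and compliance does not enter the group definitions.

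It can also be said that SAP 2.7.1 already plans a first-48-week blip subgroup and 4.6.2 already plans exact intervals. That is correct and makes the fix easier. Finally, the conflict with 4.4.1 is a separate wording matter and does not itself prove circularity.

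**Conclusion.** The point holds for the Snapshot failure test alone. If the test spans all three groups at a matched threshold and rebound takes precedence, failures fall almost only among rebounders. Under the two natural orders the test is then very likely to be significant once any failure occurs (p = 0.0001 and 0.004 with one failure in the illustration), while it carries almost no information on Blip against No Blip. The Week 96 counts behind these figures are assumptions. The containment of categories A and C follows from the SAP's own definitions. Naming a CMH test also contradicts 4.4.1 and needs reconciling in any case. The consequence is limited to a secondary, within-group descriptive display, and the primary Week 48 conclusion is untouched.

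**What to change.** 1. In SAP 4.6.2, delete the CMH p-value for Snapshot failure across any grouping that includes rebound, and show that row as counts and percentages, in line with 4.4.1.
2. State which groups are displayed, which category a subject with both a blip and a rebound enters, and which Snapshot threshold is paired with which rebound and blip threshold.
3. If the blip question is kept, use the first-48-week blip subgroup in SAP 2.7.1, restricted to subjects without rebound by Week 48. Report rebound or Snapshot failure after Week 48 by blip status with exact 95% CIs, by the Clopper-Pearson method already named in 4.6.2. Blip status is then fixed before the outcome period starts.
4. Circularity is no reason to remove the compliance or Snapshot success tests. If they stay, reconcile them with 4.4.1 and state their scores.

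The cost is a few lines of SAP text, one dropped p-value per treatment group and, if item 3 is adopted, one small table. No new data are needed.
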